Appendix 1 Schedule of Events^a

| Study Procedure | Screening | Pre-Infusion | Infusion | 2 Weeks | 1 Month | 2 Months (Phase 1 Only) | 3 Months | 6 Months | 12 Months /ET | 24, 36, 48, 60 Months Follow-Up |
|--|--------------------|--------------------|--------------------|--------------------------|--------------------------|----------------------------|--------------------------|--------------------------|------------------------------|------------------------------------|
| Study Day | Day -28 | Day 0 | Day 0 | Day 14 ±3d | Day 30 ±3d | Day 60 ±6d | Day 90 ±6d | Day 180 ±6d | Day 360 ±6d or ET | Annual ±2w |
| Relative Timing | Post-MI | ≤28d Screen | ≤28d Screen | Post Infusion | Post Infusion | Post Infusion | Post Infusion | Post Infusion | Post Infusion | Post Infusion |
| Informed Consent | X ¹ | | | | | | | | | |
| Medical History | X ¹ | X | | | | | | | | |
| Limited Physical Examination | X ² | | | | | | | | X | |
| History and Cardiac Physical | X ² | X | X | X | X | X | X | X | X | |
| Medication Review | X ¹ | X | X | X | X | X | X | X | X | |
| Adverse Events Assessment | X ² | X | X | X | X | X | X | X | X | |
| Major Adverse Cardiac Events | | | X | X | X | X | X | X | X | X |
| Vital Signs | X ² | X | X | X | X | X | X | X | X | |
| 12-Lead ECG | X ² | X | X | X | X | X | X | X | X | |
| Hematology, Chemistry, & Urinalysis | X ^{1,2} | X | X | X | X | X | X | X | X | |
| PTT / INR | | X ⁶ | | | | | | | | |
| Serum NT-proBNP | X ² | X | X | X | X | X | X | X | X | |
| Serum for Biomarkers | X ^{2,7} | | | X ⁷ | X ⁷ | X ⁷ | X ⁷ | X ⁷ | X ⁷ | X |
| Serum β-HCG | X ^{1,2,8} | | | | | | | | | |
| HIV & Hepatitis Screens; Hemoglobin A1c (HbA1c) | X ¹ | | | | | | | | | |
| Donor Specific Antibody (DSA) | X ^{2,10} | | | X ¹⁰ | X ¹⁰ | X ¹⁰ | X ¹⁰ | X ¹⁰ | X | |
| HLA Typing | X ¹⁰ | | | | | | | | | |
| ELISpot | X ¹⁰ | | | | X ¹⁰ | | | | | |
| Cardiac MRI | X ² | | | | | | | X | X | |
| Chest, Abdomen, and Pelvis CT | X ² | | | | | | | | | |
| 24 Hour Ambulatory ECG | X ² | | X ¹¹ | | X | X | | X | X | |
| Serum troponin & CK-MB | | X ⁹ | X ⁹ | X | X | | | | | |
| Echocardiography | X ² | | | | X | | | | | |
| NYHA Functional Class | X ² | | | | X | X | X | X | X | |
| Six Minute Walk Test | X ² | | | | | | | X | X | |
| Patient Questionnaires | X ^{2,12} | | | | | | | X ¹² | X ¹² | |
| Intracoronary Infusion; 24 Hr Hospitalization w/ Continuous | | | X | | | | | | | |

¹ Permitted within 28 days immediately following index MI: signing ICF, review of medical history, review of concomitant medications, and collection of laboratory samples required for assessment of study eligibility criteria (e.g., eGFR, HbA1c, hepatitis serology, HIV serology, LFTs, hematocrit, WBC, serum β-HCG and platelet count).

² Must be performed >28 days post-MI and ≤28 days of infusion. Repeat hematology, chemistry & urinalysis if initial testing to assess eligibility falls outside of this window. For post infusion, urinalysis only.

³ Every 8 hours from time of infusion until discharge.

⁴ On day of discharge.

⁵ Urinalysis only.

⁶ For subjects on anticoagulation therapy only.

⁷ Only if additional consent is obtained; collection for shipment to central laboratory.

⁸ Non-postmenopausal females only.

⁹ Troponin and CK-MB pre-infusion and approximately every 8 hours post infusion.

¹⁰ Collection of blood for testing at central laboratory.

¹¹ Starting immediately prior to discharge for 24 hours.

¹² MLHFQ, SF-36, WPAI:SHP and Patient Global Assessment.

Appendix 2 Prohibited Concomitant Medications

The following medications are prohibited for three months prior to enrollment in the study:

| GENERIC NAME | TRADE NAME |
|--|---------------|
| Abacavir | Epzicom® |
| Abacavir | Ziagen® |
| Abacavir sulfate, Lamivudine, and Zidovudine | Trizivir® |
| Adalimumab | Humira® |
| Aldesleukin | Proleukin® |
| Altretamine | Hexalen® |
| Aminoglutethimide | Cytadren® |
| Anakinra | Kineret® |
| Anastrozole | Arimidex® |
| Asparaginase | Elspar® |
| Atazanavir sulfate | Reyatax® |
| Azathioprine | Imuran® |
| Azathioprine | Azasan |
| Basiliximab | Simulect® |
| Betamethasone | Celestone® |
| Bleomycin | Blenoxane® |
| Busulfan | Myleran® |
| Capecitabine | Xeloda® |
| Carboplatin | Paraplatin® |
| Carmustine | BiCNU® (BCNU) |
| Certolizumab pegol | Cimzia® |
| Chlorambucil | Leukeran® |
| Cidofovir | Vistide® |
| Cisplatin | Platinol® |
| Cladribine | Leustatin® |
| Cortisone | Cortone® |
| Cyclophosphamide | Cytoxan® |
| Cyclophosphamide | Neosar® |
| Cyclosporine | Gengraf® |
| Cyclosporine | Neoral® |
| Cyclosporine | Sandimmune® |
| Cytarabine | Cytarabine |
| Cytarabine | DepoCyt® |
| Dacarbazine | DTIC-Dome® |

| GENERIC NAME | TRADE NAME |
|--|---------------------|
| Daclizumab | Zenopax® |
| Dactinomycin | Cosmegan® |
| Darunavir | Prezista® |
| Dasatinib | Sprycel® |
| Daunorubicin | Cerubidine® |
| Delavirdine | Rescriptor® |
| Denileukin diftitox | Ontak® |
| Dexamethasone | Dexamethasone |
| Didanosine | Videx® |
| Docetaxel | Taxotere® |
| Docetaxel | Docefrez® |
| Doxorubicin | Adriamycin® |
| Doxorubicin | Doxil® |
| Efavirenz | Sustiva® |
| Efavirenz/emtricitabine/tenofovir disoproxil | Atripla® |
| Fumarate | |
| Emtricitabine | Emtriva® |
| Emtricitabine/tenofovir disoproxil fumarate | Truvada® |
| Enfuvirtide | Fuzeion® |
| Epirubicin | Ellence® |
| Erlotinib | Tarceva® |
| Estramustine | Emcyt® |
| Etanercept | Enbrel® |
| Etoposide | Etopophos® |
| Etoposide | VePesid® |
| Etravirine | Intelence® |
| Everolimus | Afinitor® |
| Everolimus | Zortress® |
| Exemestane | Aromasin® |
| Floxuridine | Fluorodeoxyuridine® |
| Floxuridine | Ancobon® |
| Fludarabine | Oforta® |
| Fludarabine | Fludara® |
| Fosamprenavir calcium | Lexiva® |
| Gemcitabine | Gemzar |
| Golimumab injection | Simponi |
| Hydrocortisone | Cortef® |

[figure not shown]
| GENERIC NAME | TRADE NAME |
|-------------------------|-------------------|
| Hydrocortisone | Hydrocortone® |
| Hydroxychloroquine | Plaquenil® |
| Hydroxyurea | Droxia® |
| Hydroxyurea | Hydrea® |
| Idarubicin | Idamycin® |
| Ifosfamide | Ifex® |
| Imatinib mesylate | Gleevac |
| Indinavir | Crixivan® |
| Infliximab | Remicade® |
| Interferon alfa-2a | Roferon-A® |
| Interferon alfa-2b | Intron-A® |
| Interferon alfacon-1) | Inferge® |
| Interferon beta-1a | Avonex® |
| Interferon beta-1b | Betaseron® |
| Interferon beta-1b | Extavia® |
| Interferon beta-1b | Betaseron® |
| Interferon gamma-1b | Actimmune® |
| Interleukin-2 | Proleukin |
| Irinotecan | Camptosar |
| Lamivudine | Epivir® |
| Lamivudine & Zidovudine | Combivir® |
| Lanreotide | Somatuline® Depot |
| Lapatinib | Tykerb® |
| Leflunomide | Arava® |
| Lenalidomide | Revlimid |
| Letrozole | Femara® |
| Leuprolide | Lupron® |
| Leuprolide | Eligard® |
| Lomustine | CeeNu® (CCNU) |
| Maraviroc | Selzentry |
| Mechlorethamine HCl | Mustargen® |
| Megestrol | Megace® |
| Melphalan | Alkeran® |
| Mercaptopurine | Purinethol® |
| Methotrexate | Rheumatrex® |
| Methotrexate | Trexall™ |
| Methylprednisolone | Depo Medrol® |

[figure not shown]
[figure not shown]
| GENERIC NAME | TRADE NAME |
|-----------------------|---------------------|
| Methylprednisolone | Solu-Medrol® |
| Methylprednisolone | A-Methapred |
| Methylprednisolone | Medrol® |
| Mitomycin | Mutamycin® |
| Mitotane | Lysodren® |
| Mitoxantrone | Novantrone® |
| Muromonab-CD3 | Orthoclone-OKT3 |
| Mycophenolate | CellCept® |
| Nelfinavir | Viracept® |
| Nevirapine | Viramune® |
| Nilotinib | Tasigna® |
| Octreotide acetate | Sandostatin® |
| Paclitaxel | Taxol® |
| Paclitaxel | Abraxane® |
| Pazopanib | Votrient® |
| Pegaspargase | Oncaspar® |
| Peginterferon alfa-2a | Pegasys® |
| Peginterferon alfa-2b | Peg-Intron® |
| Penicillamine | Cuprimine® |
| Prednisolone | Pediapred® |
| Prednisolone | Prealone® |
| Prednisone | Meticorten® |
| Procarbazine | Matulane® |
| Raltegravir | Isentress® |
| Ribavirin | Copegus® |
| Rilonacep | Arcalyst™ |
| Ritonavir | Norvir® |
| Ritonavir/Lopinavir | Kaletra® |
| Rituximab | Rituxan® |
| Saquinavir | Invirase® |
| Sargramostim | Leukine® |
| Sirolimus | Rapamune® |
| Sorafenib | Nexavar® |
| Stavudine | Zerit® |
| Streptozocin | Zanosar® |
| Sulfasalazine | Azulfidine EN-tabs® |
| Sunitinib malate | Sutent® |

[figure not shown]
| GENERIC NAME | TRADE NAME |
|-------------------------------|-------------|
| Tacrolimus | Prograf® |
| Tamoxifen citrate | Nolvadex |
| Temozolomide | Temodar® |
| Temsirolimus injection | Torisel® |
| Teniposide | Vumon® |
| Tenofovir disoproxil fumarate | Viread® |
| Thalidomide | Thalomid® |
| Thioguanine | Tabloid® |
| Thiotepa | Thiotepa |
| Tipranavir | Aptivus® |
| Tocilizumab | Actemra® |
| Topotecan | Hycamtin® |
| Toremifene citrate | Fareston® |
| Trastuzumab | Herceptin® |
| Tretinoin | Vesanoid® |
| Tretinoin | Vesanoid® |
| Triamcinolone | Kenalog® |
| Triamcinolone | Aristospan® |
| Valrubicin | Valstar® |
| Vinblastine | Vinblastine |
| Vincristine | Vincristine |
| Vinorelbine | Navelbine® |
| Vorinostat | Zolinza® |
| Zalcitabine | Hivid® |
| Zidovudine | Retrovir® |

Appendix 3 CDC Futility Boundaries

The following four charts support DSMB safety monitoring of the Randomized Cohort. The excess for CDC-treated subjects will be of primary concern as data accrue. Charts have been prepared to correspond to accrual of 60, 120, 180, and 234 cases. The boundaries were computed using StatXact v7 (CyTel, Cambridge MA); a one-sided 95% exact test was performed assuming binomially distributed outcomes. The charts are illustrative and can be regenerated to correspond to the actual data accrued. The charts may be applied to any binary outcome pertaining to safety.

[figure not shown]

## REVISION HISTORY

Version	Date	Author(s)	Summary of Revision(s)
1.0	06Mar2017	[REDACTED]	New document

## ABBREVIATIONS

Abbreviation	Definition
6MWT	Six-Minute Walk Test
AE	adverse event
BMI	body mass index
BNP	brain natriuretic peptide
BSA	body surface area
CDC	cardiosphere derived cell
CEC	Clinical Events Committee
CI	confidence interval
CK-MB	creatine phosphokinase MB isoenzyme
CSR	Clinical Study Report
CT	computerized tomography
CTL	Cellular Technology Limited
CV	cardiovascular
DSMB	Data Safety Monitoring Board
DSA	donor specific antibodies
ECG	electrocardiogram
EDC	electronic data capture
ELISpot	enzyme-linked immunosorbent spot
EOS	end of study
FBS	fetal bovine serum
HbA1c	glycosylated hemoglobin
HBsAg	hepatitis B surface antigen
HCV	hepatitis C virus
HIV	human immunodeficiency virus
HLA	human leukocyte antigen
ICH	International Conference on Harmonisation
ICD	implantable cardioverter defibrillator
IP	investigational product
ITT	intent-to-treat
IWRS	interactive web-based system
LS	least-squares
LTfUP	Long-Term Follow-up
LV	left ventricular
LVAD	LV assist device
LVEDD	LV end diastolic diameter
LVEDV	LV end diastolic volume
LVEF	left ventricular ejection fraction
LVEDD	LV end systolic diameter
LVEDV	LV end systolic volume
M	million
MACE	major adverse cardiac event

MAR	missing at random
MedDRA	Medical Dictionary for Regulatory Activities
MFI	mean fluorescence intensity
MI	myocardial infarction
mITT	modified intent-to-treat
ML	maximum likelihood
MLHFQ	Minnesota Living with Heart Failure Questionnaire
MNAR	missing not at random
MRI	magnetic resonance imaging
NIH	National Institutes of Health
NT-proBNP	N-terminal pro-hormone brain natriuretic peptide
NYHA	New York Heart Association
PGA	Patient Global Assessment
PHA	phytohemagglutinin
PT	Preferred Term
QoL	quality of life
SAB	single antigen bead
SAE	serious adverse event
SAP	Statistical Analysis Plan
SD	standard deviation
SDF1	stromal cell derived factor 1
SF-36	Short Form - 36 questions
SOC	System Organ Class
SPRO	serious procedure related outcomes
TEAE	treatment-emergent adverse event
TFLs	tables, figures, and listings
WHO-DD	World Health Organization Drug Dictionary
WPAI:SHP	Work Productivity and Activity Impairment: Specific Health Problem

## PREFACE

The purpose of this statistical analysis plan (SAP) is to describe the planned statistical analyses and reporting for Capricor Protocol Number 1002-001. The planned analyses identified in this SAP may be included in future manuscripts. Exploratory analyses not necessarily identified in this SAP may be performed to support planned analyses. Any post-hoc or unplanned analyses not specified in this SAP will be clearly identified as such in the Clinical Study Report (CSR) and manuscripts for publication.

The SAP is a supplement to the study protocol, which should be referred to for additional details on study design, study conduct, and other operational aspects of the study.

The structure and content of the SAP provides sufficient detail to meet the requirements identified by the Food and Drug Administration and International Conference on Harmonisation (ICH) E9: Guidance on Statistical Principles in Clinical Trials. All work planned and described in the SAP will follow internationally accepted guidelines published by the American Statistical Association. The following documents were also considered in preparation for writing this SAP:

- Clinical Research Protocol 1002-01 Amendment 8.1, February 22, 2017
- ICH E3 Guideline: Structure and Content of Clinical Study Reports
- ICH E6 Guideline on Good Clinical Practice
- ICH E8 General Considerations for Clinical Trials

## 1. INTRODUCTION

The principal goal of the ALLSTAR Phase 2 trial is to establish the safety of intracoronary administration of allogeneic cardiosphere derived cells (CDCs) (CAP-1002) to shrink scar tissue 4 weeks to 12 months following myocardial infarction (MI). In parallel, signals of potential efficacy will also be evaluated. Phase 2 commenced after a Data Safety Monitoring Board had assessed one-month safety data from the Phase 1 Safety Cohort and recommended proceeding.

## 2. STUDY OBJECTIVES, TREATMENTS, AND ENDPOINTS

### 2.1 Objectives

#### 2.1.1 Primary Objectives

The primary safety objective is to test the null hypothesis that the incidence rate of the primary safety endpoint (a composite of peri-procedural clinical events) differs by no more than 0.20 between treatment groups in subjects with ischemic left ventricular (LV) dysfunction and a previous MI receiving CAP-1002 or placebo by intracoronary infusion.

The primary efficacy objective is to test the hypothesis that, in subjects with ischemic LV dysfunction and a previous MI, CAP-1002 by intracoronary infusion is superior to placebo in reducing infarct size, expressed as a percent of LV mass, 12 months after infusion, either in all subjects combined or in subjects with recent MI (<= 90 days before infusion).

#### 2.1.2 Secondary Objectives

The secondary safety objective is to compare the safety profiles of CAP-1002 and placebo over 12 months based on pre-specified clinical events and development of increased human leukocyte antigen (HLA) antibody levels.

The secondary efficacy objective is to compare CAP-1002 and placebo treatment groups at 6 and 12 months post-infusion on endpoints related to LV function and structure, clinical function and status, and cardiac biomarkers.

### 2.2 Treatment Group Comparisons

Two treatment groups will be compared in the study:

- CAP-1002 (single administration of 25 M cells)
- Placebo

### 2.3 Study Endpoints and Hypotheses

#### 2.3.1 Primary Safety Endpoint

The primary safety endpoint is whether or not any of the following adjudicated (see [Section 12](#)) events occur during the one month post intracoronary infusion:

1. Acute myocarditis possibly attributable to the investigational product (IP), diagnosed with consideration of clinical context, with or without a clinically indicated endomyocardial biopsy. In order to be considered related to the IP, humoral or cellular immune reaction specific to CAP-1002 must also be documented for subjects treated with CAP-1002, or a temporal relationship with IP administration must exist for subjects administered placebo. See [Section 12](#) for further information related to blinded adjudication by the Clinical Events Committee (CEC).
2. Death due to ventricular tachycardia or ventricular fibrillation defined as occurring with electrocardiogram (ECG) documentation of these arrhythmias during ambulatory ECG monitoring in an outpatient setting or during routine ECG monitoring while hospitalized.
3. Sudden unexpected death defined as occurring within one hour of symptom onset, or unwitnessed death in a person previously observed to be well within the preceding 24 hours without an identified cause.
4. Major adverse cardiac event (MACE), defined as the composite incidence of death, nonfatal recurrent MI, hospitalization with primary discharge diagnosis of heart failure, emergency room treatment for heart failure [ N-terminal pro-hormone brain natriuretic peptide (NT-proBNP)  $> 450$  pg/mL or brain natriuretic peptide (BNP)  $> 100$  pg/ml, with treatment including intravenous diuretic administration], LV assist device (LVAD) placement or heart transplant. Peri-infusion MI will be defined as presence of troponin or creatine phosphokinase MB isoenzyme (CK-MB) levels  $> 5$  times the upper reference limit during the 24 hours following infusion. These elevations must be accompanied by symptoms of ischemia  $> 20$  minutes in duration and ECG changes indicative of new ischemia (new ST-T changes or new left bundle branch block), development of pathological Q waves on the ECG, imaging evidence of new loss of viable myocardium, or new regional wall motion abnormality.

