4. Percent change and change from baseline in MRI assessment of infarct size expressed in grams
5. Percent change and change from baseline in MRI assessment of viable mass expressed in grams

Regional measure

6. Percent change and change from baseline in MRI assessment of function in the region which received CAP-1002 therapy

Clinical function/status measures

7. Percent change and change from baseline in distance covered in six minute walk test
8. Change from baseline in Minnesota Living with Heart Failure Questionnaire (MLHFQ) scores (Total score, Physical Dimension score, and Emotional Dimension score)
9. Change from baseline in Patient Global Assessment (PGA) score

Biomarker

10. Percent change and change from baseline in NT-proBNP
11. Change from baseline in log transformed NT-proBNP

Additional detail regarding secondary endpoint analyses can be found in the Statistical Analysis Plan (SAP).

Statistical Methods:

The safety analysis population will consist of all subjects who received an infusion of either CAP-1002 or placebo. The primary efficacy analysis population in the Randomized Cohort (Primary Modified Intent-to-Treat (mITT) Population, Exploratory mITT Population) will consist of all subjects in the Safety Population who had a baseline observation and at least one post-baseline observation. Demographics and baseline characteristics will be summarized and reported. The Safety Cohort subjects will be summarized and analyzed distinctly from the Randomized Cohorts due to the unblinded nature of the treatment intervention. Similarly, the Exploratory Randomized Cohort of mismatched subjects will also be summarized distinctly from the Primary Randomized Cohort. Details on additional analysis populations will be addressed in the SAP.

Alpha for the study will be controlled by using a closed testing procedure. The primary efficacy analyses will be performed for the analysis population using a modified intent-to-treat population with post-baseline outcome data using a longitudinal mixed effects model. The final analysis will test the hypothesis after 12 months of treatment.

Primary Safety Endpoint: Point estimates and confidence intervals of the proportion of subjects that experience acute myocarditis possibly attributable to CAP-1002 (diagnosed with consideration of clinical context and accompanied by humoral or cellular immune reaction

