specific to CAP-1002), death due to ventricular tachycardia or ventricular fibrillation, sudden unexpected death, or a major adverse cardiac event (MACE), defined as the composite incidence of death, non-fatal recurrent MI, hospitalization for heart failure, emergency room treatment for heart failure (NT-proBNP >450 pg/mL or BNP >100 pg/ml, with treatment including intravenous diuretic administration), left ventricular assist device (LVAD) placement or heart transplant within the first month post-infusion will be calculated.

Secondary Safety Endpoints: Descriptive analyses of all secondary safety endpoints will be performed using percentages, means, and ranges where appropriate. For incidence rates, two-sided 95% confidence intervals will be constructed for the differences between CAP-1002 and placebo and a two-sided Fisher Exact test will be used for between-treatment comparisons; the Wilcoxon-Mann-Whitney test will be used to compare distributions and ordinal outcomes between randomized treatments. There will be no adjustments for multiple safety assessments by the DSMB and at the interim analyses; a two-sided $p=0.05$ will be used to establish statistical significance.

Primary Efficacy Endpoint: The primary efficacy endpoint is the percent change from baseline in MRI assessment of infarct size as a percent of left ventricular mass 12 months after administration of treatment (either CAP-1002 or placebo). The primary efficacy hypothesis is that CAP-1002 is superior to placebo in reducing infarct size in either all subjects combined (“full group”) or in subjects with recent MI (“subgroup”). A closed testing procedure will be used so that strong control of type 1 error is maintained.

The primary analysis will be a longitudinal mixed effects model. The response variable of percent change from baseline in infarct size as a percent of left ventricular mass will be modeled with the fixed categorical effects of treatment group and time (6 and 12 months), as well as a continuous fixed covariate of baseline infarct size. Intercept and subjects will be treated as random in this mixed effects model. The primary hypothesis will be tested using the estimated treatment effect compared to placebo at 12 months. An additional test will compare the treatments at 6 months and will be considered secondary. Model results will be provided for fixed affects and estimates for each level of each affect.

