7.4.3 Relationship

The Investigator is obligated to assess the relationship between study therapy and the occurrence of each AE/SAE. The Investigator will use clinical judgment to determine if there is a reasonable possibility that the pharmacological action of the study agent was responsible for the AE/SAE being reported. Alternative causes such as natural history of the underlying diseases, concomitant

therapy, other risk factors, and the temporal relationship of the event to the study agent will be considered and investigated. The Investigator will also consult the Investigator's Brochure and/or Product Information, for marketed products, in the determination of his/her assessment.

All AE/SAE that occur during the course of the clinical study will be evaluated and a determination of relatedness to the investigational product or procedure will be defined according to one of the following categories:

- Definite: The AE/SAE is clearly related to the investigational product or procedure.
- Probable: The AE/SAE is likely related to the investigational product or procedure.
- Possible: The AE/SAE may be related to the investigational product or procedure. All AEs and SAEs that occur within 24 hours of intervention will, because of the temporal relationship, be considered as at least possibly related to the investigational product or procedure and will be reported to the DSMB.
- Unlikely: The AE/SAE is doubtfully related to the investigational product or procedure.
- Unrelated: The AE/SAE is clearly NOT related to the investigational product or procedure.

There may be situations when an SAE has occurred and the Investigator has minimal information to include in the initial report. However, it is very important that the Investigator make an assessment of causality.

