### **2.3.2 Primary Safety Endpoint Hypothesis**

For the primary safety endpoint, the following hypothesis set will be tested:

$$H_0: p_c - p_p \geq 0.20$$

$$H_a: p_c - p_p < 0.20$$

where  $p_c$  and  $p_p$  are the proportions of subjects in the CAP-1002 and placebo treatment groups, respectively, who experienced the primary safety endpoint.  $H_0$  will be rejected if the upper limit of the 90% confidence interval (CI) for  $p_c - p_p$  is less than 0.20.

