## 10.1 Primary Safety Endpoint

The primary safety endpoint is a composite indicator variable, as described in [Section 2.3.1](#). The primary safety endpoint listing will include indicators for each component of the endpoint and for the endpoint itself; similarly, each component and the endpoint itself will be summarized as frequency and percentage of subjects, 90% CIs for both treatment groups, a 90% CI for the difference in proportions between treatment groups, and the p-value from an equivalence Wald test of  $H_0$ .

Since the primary safety endpoint is based on events that occur immediately after IP infusion and safety analyses are done only in subjects who were infused, handling of missing data is not applicable.

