### 10.3 AEs

AEs reported from screening through EOS will be coded according to MedDRA® (Medical Dictionary for Regulatory Activities) version 18.1. Each reported AE will be mapped to a Preferred Term (PT) and a System Organ Class (SOC). A subset of AEs (indicated below) will be adjudicated by the independent CEC.

A TEAE will be defined as an AE that began or worsened after the time of vascular access. AEs with insufficient date or time information to determine whether or not they were treatment-emergent will be considered treatment-emergent and the ambiguity regarding start time/date for these AEs will be footnoted in summary tables.

All reported TEAEs will be listed. Separate listings will be done for deaths, non-treatment-emergent AEs and serious AEs (SAEs), treatment-emergent SAEs, TEAEs within 24 hours of IP administration (adjudicated if related to IP or procedure), and TEAEs that resulted in study discontinuation (excluding deaths). Treatment-emergent SAEs will be adjudicated. The listing of deaths will include most appropriate category of death (e.g., CV, cerebrovascular, infection, malignancy, trauma/accident) and whether or not an autopsy was performed.

Incidence and number of TEAEs will be summarized by SOC and PTs within SOCs, both overall and by relationship to IP, relationship to IP administration, and severity. Relationship status “possibly,” “probably,” or “definitely” will be considered related and will be adjudicated. Missing relationship will be considered related and missing severity will be considered severe; the lack of assigned relationships for these AEs will be footnoted in summary tables. Only the most related TEAE per subject for a given PT will be counted in summaries by relationship; similarly, only the most severe TEAE will be counted in summaries by severity. Separate summaries will be done for TEAEs within 24 hours of IP administration (adjudicated if related to IP or procedure), treatment-emergent SAEs, treatment-emergent deaths, and TEAEs resulting in study discontinuation (excluding deaths). Each summary table will include a p-value for the comparison of incidence for each SOC and PT, as well as overall, between treatment groups. Product limit estimates of median time to death and 95% CIs will be calculated.

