## 12. CLINICAL EVENTS COMMITTEE

In order to apply some level of consistency and standardization, the following will be adjudicated by a CEC:

- Primary and secondary safety endpoints with the following exceptions:
  - The CEC will refer any potential case of acute myocarditis to the DSMB in order to make a final ruling on whether the clinical event meets the protocol-defined definition of acute myocarditis. The DSMB will be unblinded to humoral and cellular immunology data.
  - Development of increased anti-HLA antibody levels with development of sensitization to HLA antigens specific to the CAP-1002 CDC donor. The DSMB clinical immunologist will be unblinded to all available DSA data during the conduct of the trial.
- AEs occurring within 24 hours of IP administration.
- AEs judged by the investigator as possibly, probably or definitely related to the IP or IP administration procedure, reported at any time.
- Treatment-emergent SAEs.

The CEC will follow consensus definitions of CV endpoint events. In the case where the protocol explicitly provides an endpoint definition, the CEC will adjudicate the clinical event according to the protocol definition and then, separately, according to the consensus definition. In the case where the protocol provides only a partial definition (e.g., “emergency room treatment for heart failure”) or is silent on the definition of the endpoint, the consensus definition, if it exists, will be used.

For safety endpoints, a hierarchy will be applied for a clinical event that could be adjudicated in multiple categories so that a clinical event is counted only once. The hierarchy, from highest severity to lowest, will be death > heart failure hospitalization > CV-related hospitalization. Any adjudicated event not otherwise named in the consensus definitions will be MedDRA-coded.

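### The primary safety endpoint counts acute myocarditis by a different rule in each arm, and SAP 10.1 has no sensitivity analysis under one common rule

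*SAP*

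**What the plan says.** Item 1 of the primary safety endpoint (SAP 2.3.1; same rule in Protocol 2.4 and 9.5.1 and in the Safety Assessments part of the synopsis) is acute myocarditis possibly attributable to the investigational product. The test of relatedness has two branches: "humoral or cellular immune reaction specific to CAP-1002 must also be documented for subjects treated with CAP-1002, or a temporal relationship with IP administration". The second branch is the one for placebo. So a CAP-1002 case needs a documented product-specific immune reaction, and a placebo case needs only a link in time.

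The test is in SAP 2.3.2. The null hypothesis that the CAP-1002 proportion exceeds the placebo proportion by 0.20 or more "will be rejected if the upper limit of the 90% confidence interval (CI) for" the difference is below 0.20. SAP 10.1 adds that "each component and the endpoint itself will be summarized as frequency and percentage of subjects, 90% CIs for both treatment groups", with a 90% interval for the difference and a Wald test. All of this uses the definition in SAP 2.3.1.

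On adjudication, SAP 12 states: "The CEC will refer any potential case of acute myocarditis to the DSMB in order to make a final ruling". That ruling is against the protocol definition. The DSMB sees the immunology data; SAP 5 keeps the CEC blinded to treatment. Where the protocol defines an endpoint, SAP 12 also has the CEC adjudicate separately by a consensus definition.

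**The concern.** The two proportions in the 0.20 test are counted by different rules, in the component most specific to an allogeneic cell product. A CAP-1002 subject with clinically diagnosed myocarditis but a negative, missing or inconclusive immune result is not counted under item 1. A placebo subject with the same picture is counted if the timing fits, and within one month of infusion it usually will. If so, the estimated excess is too small and the test leans towards the reassuring conclusion.

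Nothing else in the plan supplies a one-rule version of the test. The DSMB ruling applies the same definition. SAP 10.1 does not use the consensus adjudication. The adverse event tables ("Each summary table will include a p-value for the comparison of incidence for each SOC and PT") compare the arms by preferred term but do not feed the 0.20 test.

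**Working it through.** **Inputs from the documents.** The synopsis gives about 69 CAP-1002 and 34 placebo subjects in the Primary Randomized Cohort (103 × 2/3 = 68.7 and 103/3 = 34.3). The rule is a 90% Wald upper limit below 0.20 (z = 1.645). The documents give no event rate or power for this endpoint, so there is no figure of the plan's own to reproduce.

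**Assumed inputs.** m is the one-month rate of clinical myocarditis that meets no other component, equal in both arms: 1%, 2% or 5%. s is the share of CAP-1002 cases with a documented immune reaction: 0.75, 0.50 or 0.25. q is the share of placebo cases judged temporally related: 1 or 0.5.

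**Direction.** Relative to counting every clinical case, the CAP-1002 proportion falls by m(1 − s) and the placebo proportion by m(1 − q). The difference therefore shifts by −m(1 − s) + m(1 − q) = m(s − q). This is negative if s < q, zero if s = q and positive if s > q. With unequal rates it is −m_c(1 − s) + m_p(1 − q).

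**Decision boundary.** Upper limit = d + 1.645 × √[p_c(1 − p_c)/69 + p_p(1 − p_p)/34], with d = p_c − p_p.
- 9/69 v 0/34: 0.1304 + 1.645 × √(0.1304 × 0.8696/69) = 0.197, pass; 10/69 v 0/34: 0.215, fail.
- 10/69 v 1/34: 0.19996, pass; 11/69 v 1/34: 0.217, fail.
- 3/69 v 1/34: 0.077; 6/69 v 1/34: 0.131. Both are far below 0.20.

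**At the margin.** Take true rates of 25% and 5% with all clinical myocarditis counted. The counted rates become 0.25 − m(1 − s) and 0.05 − m(1 − q). Exact enumeration of all 70 × 35 outcomes gives P(conclude below 0.20) = 5.6% under one common rule. Under the plan's rule, for s from 0.75 to 0.25:

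| m | q = 1: shift (points) | q = 1: P | q = 0.5: shift (points) | q = 0.5: P |
|---|---|---|---|---|
| 1% | −0.25 to −0.75 | 6.1–7.1% | +0.25 to −0.25 | 5.3–6.3% |
| 2% | −0.5 to −1.5 | 6.6–9.0% | +0.5 to −0.5 | 5.1–7.2% |
| 5% | −1.25 to −3.75 | 8.4–17.3% | +1.25 to −1.25 | 4.5–10.7% |

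The 5% row is an extreme: with a 5% placebo rate it makes every placebo event a myocarditis.

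**Away from the margin** (m = 2%, s = 0.5, q = 1). At an assumed 5% v 5%, P(conclude below 0.20) is 0.9994 under one rule and 0.9999 under the plan's rule. At 8% v 5% it is 0.983 and 0.993.

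**The case against.** The rule is a deliberate attribution criterion. The component targets myocarditis attributable to the product, and placebo contains no cells, so a CAP-1002-specific immune reaction cannot serve as the attribution test there. That stands, and is why the endpoint should stay.

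The direction is a judgement. With q = 0.5 the shift is symmetric about zero over the assumed range of s, so a probably downward shift depends on q being near 1. That also stands. A reader might infer that the rule is certain to favour CAP-1002; the documents do not support it. A reader might also note that ELISpot is planned in only 36 of about 69 randomised CAP-1002 subjects (Protocol 6.5.2) and infer that about half the cases could not be confirmed. That does not follow: a humoral reaction suffices, donor-specific antibodies are measured in all subjects at Week 2 and Month 1, and the DSMB can extend ELISpot.

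The Statistical Methods part of the synopsis shortens the component to "acute myocarditis possibly attributable to CAP-1002 (diagnosed with consideration of clinical context and accompanied by humoral or cellular immune reaction" specific to CAP-1002, with no placebo branch. Read alone, it might suggest a contradictory rule with bias the other way. It is an abbreviation: the same synopsis states both branches in full under Safety Assessments. Aligning it is editorial.

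Uncounted cases are not hidden. Those with death, heart failure hospitalization, LVAD or transplant count through MACE in both arms, others appear in the adverse event tables, and every potential case reaches the DSMB. This limits the harm, but none of it re-runs the 0.20 test.

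Finally, a procedures manual for adjudication and a DSMB charter exist but were not available. They may define the temporal relationship (Protocol 7.4.3 ties it to 24 hours, for adverse event causality only) and the antibody level that counts as documented. The absence of those details here is not evidence that they are undefined.

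**Conclusion.** The concern holds as a minor one. The arm-specific rule is in the text, the 0.20 test is planned under that rule only, and no other element of the plan supplies a common-rule test. The likely effect is a small downward shift in the estimated excess, because most cases within a month would be called temporally related. The shift depends on m, s, q and equal myocarditis rates in the two arms, all assumed.

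The effect matters only if the true excess is close to 0.20: the error rate then moves from 5.6% to 6.1–9.0% for m of 1 to 2% with q = 1. At low event rates the conclusion is practically unaffected. A reader might go further and infer that a conclusion of less than 0.20 would be invalid; these figures do not support that. What is missing is a planned check that the conclusion does not depend on the arm-specific rule.

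**What to change.** Keep the protocol endpoint. In SAP 10.1, pre-specify one sensitivity analysis of the composite and of the myocarditis component. It should count all clinically adjudicated acute myocarditis within one month in both arms, regardless of immune findings, against the same 0.20 margin. In SAP 12, have the blinded CEC record its ruling on the clinical diagnosis before it refers the case to the DSMB.

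The cost is one extra analysis, a small change to SAP 12 (and possibly to the adjudication manual) and one extra recorded ruling per potential case. No new subject assessments are needed. The downside is that some myocarditis unrelated to the cells (Protocol 7.3.2 lists such causes) is counted, but by the same rule in both arms. If it is added only after results are known, the analysis would have to be labelled post hoc under the SAP preface.

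As text clarifications, worth making at the same time but not part of the point: state what counts as a temporal relationship for this component, say whether the 5000 or the 1000 MFI threshold in SAP 2.3.3 applies to it, and align the shortened synopsis wording with the full definition.
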